## 1.4 Risk-Benefit Assessment

This is an observational study with no drug intervention. The risks in this study are minimal, given that assessments are based on a single blood sample and a single urine sample for subjects in Part A. Subjects progressing to Part B will provide a maximum of 2 additional blood samples and 2 additional urine samples taken at 2 subsequent monthly visits. The risks involved in collecting venous blood samples may include possible bruising, redness and swelling around the site of blood withdraw; bleeding at the site; feeling of light-headedness when the blood is drawn; and rarely, an infection at the site. Results of urine assessments relative to buprenorphine and other opioids will remain confidential.

The study does not provide direct benefit to the study subjects; however the results of the study will inform patients and physicians on how long buprenorphine remains at quantifiable concentrations in plasma after the last dose of SUBLOCADE, as well as clarifying the relationship with positive UDS for buprenorphine.

Based on ongoing review of the data, the Sponsor reserves the right to modify the duration of the study at any time.

The study will be carried out in accordance to the protocol and with local legal and regulatory requirements, International Council for Harmonisation E6 / Good Clinical Practice (ICH/GCP) guidelines and all applicable subject privacy requirements.

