### **8.4 Safety Assessments**

All adverse events (AE) associated with study assessments and/or study conduct will be collected using the Adverse Event eCRF. All serious AEs (SAEs) associated with the study assessments and/or study conduct will be collected using the Safety Information Collection Form.

Concomitant medications will be collected, including any prescribed MAT (inclusive of any MATs that lead to study discontinuation, such as long-acting buprenorphine treatment).

Illicit use of buprenorphine will be captured separately outside of the Concomitant Medication eCRF.

See Section 12 for details of pregnancy assessments.

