## 10 ADVERSE EVENTS

The Investigator or designee is responsible for identifying, documenting and reporting events that meet the definition of an AE.

deat

In addition, any AE or SAE of which the Investigator becomes aware that pertains to SUBLOCADE or SUBOXONE use, or related to participation in a previous SUBLOCADE clinical study, will be reported via completion of the Safety Information Collection Form and that form will be sent to the following email address: [[contact]](mailto:[contact]).

Events meeting the definition of an AE associated with study assessments and/or study conduct include the following:

- new condition detected after study assessment and/or associated with study conduct even though the AE may have been present prior to the study assessment or study participation;
- exacerbation of a pre-existing condition (including intensification of a condition and/or an increase in frequency) resulting from a study assessment and/or study conduct;
- any safety assessments resulting from a study assessment and/or study conduct felt to be clinically significant in the opinion of the Investigator (including those that worsen from baseline);
- symptoms and/or clinical sequelae resulting from a study assessment and/or study conduct that resulted in intervention.

Events that do not meet the definition of an AE include:

- the disease/disorder being studied, or expected progression, signs, or symptoms of the disease being studied, unless more severe than expected for the subject's condition;
- medical or surgical procedures; the condition that leads to the procedure is an AE;
- situations where an untoward medical occurrence did not occur (e.g., social and/or convenience admission to a hospital, hospitalization for elective surgery, hospitalization for observation in the absence of an AE);
- anticipated day-to-day fluctuations of pre-existing disease(s) or condition(s) present or detected at the start of the study that do not worsen.

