## **10.1 Assessment of Adverse Events**

The Investigator is ultimately responsible for assessing and reporting all AEs as outlined in the protocol. The assessment and reporting of AEs may be delegated to a medically qualified sub-Investigator, trained on this study protocol, who is listed on the delegation of authority log.

Adverse events should be volunteered by the subject or obtained from observation of the subject at a site visit. If an event requires intervention, or if in the opinion of the Investigator it is clinically significant, then it will be reported as an AE (using the Adverse Event eCRF).

All AEs are to be assessed and recorded in a timely manner and followed to resolution or until the Investigator determines that there is not an anticipated resolution. Each AE is to be documented with reference to severity, date of occurrence, duration, treatment and outcome. Furthermore, each AE is to be classified as being serious or non-serious.

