### **10.1.2 Assessment of Intensity**

The term "severe" is used to describe the intensity (severity) of a specific event (as in mild, moderate or severe); the event itself, however, may be of relatively minor medical significance (such as a severe headache). This is not the same as "serious," which is based on subject/event outcome or action criteria usually associated with events that pose a threat to a subject's life or functioning. Seriousness (not severity) serves as a guide for defining regulatory reporting obligations.

- Mild: Causes transient or mild discomfort; no limitation of usual activities; no medical intervention required.
- Moderate: Causes mild to moderate limitation in activity; some limitation of usual activities; no or minimal medical intervention or therapy is required.
- Severe: Causes marked limitation in activity; some assistance is usually required; medical intervention or therapy is required; hospitalization is probable.

Adverse events with changes in severity should be documented as separate events.

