#### 6.1.2 Safety Analysis Set

**Safety Analysis Set Part A:** The Safety Analysis Set Part A consists of all subjects who have completed at least one blood or urine sample collection in Part A (from Scheduled or Unscheduled visits).

**Safety Analysis Set Part B:** The Safety Analysis Set Part B consists of all subjects who have completed at least one blood or urine sample collection in Part B (from Scheduled or Unscheduled visits).

The **Safety Analysis Set** consists of all subjects who are part of the Safety Analysis Set Part A and/or Part B.

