## 12. SAFETY ANALYSES

### 12.1 ADVERSE EVENTS

Only adverse events (AEs) associated with study assessments and/or study conduct will be collected using the Adverse Event eCRF. If any of these AEs become serious AEs (SAEs), they will be reported to Indivior via the Safety Information Collection Form.

Adverse events associated with study assessments and/or study conduct (AE onsets on or after the first visit in this study) will be coded using the most up-to-date version of the MedDRA dictionary, and grouped by primary SOC. These events will be summarized with frequency and percentage, by SOC and PT, by the cohorts of Part A and Part B within the Safety Analysis Set, with separate summaries for all AEs, AEs related to study procedures (such as urine collection procedure or blood collection procedure), and serious AEs. The incidence of deaths will also be reported.

Since there is no study drug for this study, no treatment emergent AE is defined for this study.

A summary of AEs will be presented by the cohorts of Part A and Part B within the Safety Analysis Set, including the number and percentage of subjects reporting at least one AE, the number and percentage of subjects with the following:

- AE summary
- All AEs by SOC and PT
- All AEs by SOC, PT and severity
- SAEs
- SAEs by SOC, PT and severity

A breakdown of the number and percentage of subjects reporting each AE categorized by SOC and PT coded per the MedDRA dictionary version or later version available during study will be presented by the cohorts of Part A and Part B within the Safety Analysis Set. Note that counting will be by subject not by event, and subjects will be only counted once within each SOC or PT.

A summary of events reported, categorized by severity, will also be provided by the cohorts of Part A and Part B within the Safety Analysis Set. Subjects with multiple events within a SOC or PT will be counted under the category of their most severe event within that SOC or PT. A further tabulation of severe AE will be presented by SOC and PT.

Additionally, all AEs will be summarized by maximum severity (mild, moderate, or severe).

AE will also be listed for all subjects in the Safety Analysis Set, variables will be added to indicate if the subject belongs to the Safety Analysis Set Part A, Safety Analysis Set Part B, FAS Part A and FAS Part B.

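### The protocol gives two recording rules for adverse events, and under one of them mild blood-draw events reach the SAP safety tables only if the Investigator judges them clinically significant

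*Protocol*

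**What the plan says.** Several places set no threshold for recording an adverse event (AE):

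- Protocol 8.4: "All adverse events (AE) associated with study assessments and/or study conduct will be collected using the Adverse Event eCRF".
- Footnote g to the Schedule of Events limits eCRF collection only by relation to study procedures or conduct. SAP Appendix 1 repeats the footnote.
- Protocol Section 10, first bullet of the AE definition, counts a "new condition detected after study assessment and/or associated with study conduct", with no test of intervention or significance.
- Protocol 10.1, third paragraph: "All AEs are to be assessed and recorded in a timely manner".

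Other places do set one:

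- Protocol 10.1, second paragraph: "If an event requires intervention, or if in the opinion of the Investigator it is clinically significant, then it will be reported" as an AE on the Adverse Event eCRF.
- Protocol Section 10, third bullet, covers safety assessments that the Investigator finds clinically significant. The fourth covers symptoms or sequelae that led to intervention.

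Protocol 10.1.2 sets the lowest grade: "Mild: Causes transient or mild discomfort; no limitation of usual activities; no medical intervention required". Protocol 1.4 names the expected risks of the blood draw: "possible bruising, redness and swelling around the site of blood withdraw", bleeding, light-headedness and, rarely, infection.

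SAP 12.1 tabulates AEs by system organ class and preferred term and by worst severity, with a mild category. The tables use the Safety Analysis Set, which for Part A is "all subjects who have completed at least one blood or urine sample collection in Part A".

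**The concern.** Two rules govern one form. If every procedure-related AE already goes on the eCRF, a sentence naming two conditions for reporting on that eCRF adds nothing unless it is a threshold. A site coordinator is therefore likely to read it as one. A mild event cannot meet the intervention condition by definition, so its entry would rest on an opinion for which the protocol gives no criteria.

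The study gives no drug, and its safety tables mainly describe the effects of drawing blood and collecting urine. Sites that follow 8.4 and sites that follow 10.1 would supply different data to the same table, and a reader could not tell a low event rate from a high recording threshold. Events not written down at the visit cannot be recovered at analysis.

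A smaller, related point is that the Safety Analysis Set requires a completed collection, whereas AE collection starts at consent (Protocol 10.1.1).

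**Working it through.** **Step 1. Follow one event through the rules.** Take a small bruise after the Visit 1 draw that limits nothing and needs no treatment.

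| Place | Is the bruise entered on the AE eCRF? |
|---|---|
| Protocol 8.4 | Yes |
| Footnote g | Yes |
| Section 10, bullet 1 | Yes, as a new condition |
| Section 10, bullet 4 | Does not qualify here, as there was no intervention |
| 10.1, third paragraph | Yes, if it already counts as an AE |
| 10.1, second paragraph, read as a threshold | Only if judged clinically significant |

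Under 10.1.2 the bruise is mild, so it fails the intervention condition by definition. The same event is therefore recorded or not according to which section the site follows.

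**Step 2. Scale, for illustration only.** The plan states no AE rate, so there is no figure to reproduce.

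Inputs from the documents: about 60 subjects in Part A with one draw each, and at most 30 in Part B with two further draws (Protocol 5.1 and the Schedule of Events). The maximum number of draws is 60 + 2 × 30 = 120. SAP 12.1 counts subjects, so the Part A denominator of 60 is used.

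Assumptions, not in the documents: *r* is the share of subjects with a mild blood-draw event, and *f* is the share of those events the Investigator calls clinically significant. *f* = 1 corresponds to full recording.

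Expected subjects in the table = 60 × *r* × *f*. Chance that at least one appears = 1 − (1 − *r f*)^60.

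| *r* | *f* = 1 | *f* = 0.25 | *f* = 0.1 |
|---|---|---|---|
| 5% | 3.0 (0.954) | 0.75 (0.530) | 0.3 (0.260) |
| 10% | 6.0 (0.998) | 1.5 (0.781) | 0.6 (0.453) |
| 20% | 12.0 (1.000) | 3.0 (0.954) | 1.2 (0.702) |

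Each cell gives the expected number of subjects, with the chance of at least one in brackets. At *r* = 10%, for example, 60 × 0.10 × 0.25 = 1.5 and 1 − 0.975^60 = 0.781.

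**Step 3. The Safety Analysis Set.** A Part A subject whose draw is abandoned and who gives no urine, including at any unscheduled visit, has no completed collection. That subject is outside the set, and any AE from the attempt is outside the SAP 12.1 tables. Protocol 14.3 uses all enrolled subjects for all analyses, and SAP Section 17 declares only the rewording of the Full Analysis Set. A Part B subject with no completed Part B collection stays in the overall set through Part A but leaves the Part B set.

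**The case against.** A reader might infer that 10.1 reports an event only if it needs intervention or is significant, so that mild events vanish from the tables. The documents do not support that. The sentence gives a sufficient condition and excludes nothing. The same section asks for all AEs to be recorded. Section 8.4, footnote g and the first bullet of Section 10 would each take in a bruise from the draw. Even under the strict reading, a mild event can enter as clinically significant. This objection stands: mild events can be lost, but it is not established that they will be.

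A reader might also infer a specific distortion, such as a severity table shifted towards moderate, or a count of 0/60 taken as proof of a rate below 6.0% (exact two-sided 95% limit, 1 − 0.025^(1/60)). Neither follows. Moderate events are themselves defined as needing little or no intervention, so some would face the same test. Protocol 14.1 rules out confidence intervals, so no planned output would make the second claim, and a true rate of 5% would lie inside that limit anyway.

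Nor can every unrecorded bruise be put down to 10.1. A subject who leaves after Visit 1 may take part for one day (Protocol 4.3), and AE collection ends with the last visit (10.1.1). A non-serious effect that appears later is missed under either rule.

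On the Safety Analysis Set, exclusion needs both collections to fail, which should be rare. Protocol 14.1 also promises listings for everyone enrolled, although SAP 12.1 restricts the AE listing to the Safety Analysis Set.

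Finally, safety is not a stated objective. That limits the weight of the point, but the SAP still plans these tables and they need one definition of what is counted.

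**Conclusion.** The concern holds as an internal inconsistency. Protocol 8.4, footnote g and the first bullet of Section 10 set no threshold. The second paragraph of 10.1 can naturally be read as setting one, and the third and fourth bullets of Section 10 carry similar thresholds. Under that reading, mild blood-draw events depend on Investigator opinion, so they can be under-recorded or recorded unevenly across sites. The bias in SAP 12.1 is downward for mild events.

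Its size cannot be derived from the documents. The table above rests on assumed values of *r* and *f* and shows only that the count would be sensitive to the recording rule. Near-total loss of mild events is the extreme case (*f* close to 0), not the expected one. The primary endpoint, a plot of plasma concentrations, is unaffected. The Safety Analysis Set issue is secondary and marginal.

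**What to change.** Reconcile Protocol 8.4, 10, 10.1 and footnote g into one recording rule. Replace the conditional sentence in 10.1 with: *Every AE associated with study assessments or study conduct is recorded on the Adverse Event eCRF, whatever its intensity and whether or not intervention was required.* Align the fourth bullet of Section 10, so that a symptom such as light-headedness does not need to have led to intervention to count.

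In SAP 6.1.2, for Parts A and B, define membership by having had at least one blood or urine sample collection *attempted* rather than completed. A subject with an abandoned draw and no urine then stays in the AE tables.

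The cost is a protocol amendment (Protocol Section 17), a SAP wording change, a note in the eCRF completion guidelines, and a few more minor events to enter. No sample, visit or PK analysis changes.

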### **10.1.1 Time Period for Collecting Adverse Events**

Adverse events will be collected from the time of signed informed consent until completion of the subject's last visit.

Subjects with SAEs related to study procedures ongoing at the end of the study or after early termination will be followed by the Investigator until stabilization or resolution. If a subject experiences the onset of an SAE assessed by the Investigator as related to study procedures within a period of 30 days following study completion or withdrawal, the Investigator will follow the procedures defined in Section 10 and Section 11 for assessing, documenting, and reporting these events.

### **10.1.2 Assessment of Intensity**

The term "severe" is used to describe the intensity (severity) of a specific event (as in mild, moderate or severe); the event itself, however, may be of relatively minor medical significance (such as a severe headache). This is not the same as "serious," which is based on subject/event outcome or action criteria usually associated with events that pose a threat to a subject's life or functioning. Seriousness (not severity) serves as a guide for defining regulatory reporting obligations.

- Mild: Causes transient or mild discomfort; no limitation of usual activities; no medical intervention required.
- Moderate: Causes mild to moderate limitation in activity; some limitation of usual activities; no or minimal medical intervention or therapy is required.
- Severe: Causes marked limitation in activity; some assistance is usually required; medical intervention or therapy is required; hospitalization is probable.

Adverse events with changes in severity should be documented as separate events.

### 10.1.3 Assessment of Causality

The Investigator or a medically qualified sub-Investigator, trained on this study protocol and listed on the delegation of authority log, is responsible for determining the AE relationship to study assessments and/or study conduct.

The following categories will be used to define the relationship of an AE to study assessments/conduct:

- Not Related: Data are available to identify a clear alternative cause for the AE other than assessments/conduct.
- Related: The cause of the AE is related to assessments/conduct, and cannot be reasonably explained by other factors (e.g., the subject's clinical state, concomitant therapy, and/or other interventions).

A “reasonable possibility” is meant to convey that there are facts/evidence or arguments to suggest a causal relationship, rather than that a relationship cannot be ruled out. The Investigator will use clinical judgment to determine the relationship. Alternative causes, such as natural history of the underlying diseases, concomitant therapy, other risk factors and the temporal relationship of the event to study assessments will be considered and investigated. The Investigator will also consult Product Information in the determination of his/her assessment. For each AE/SAE reported, the Investigator must document in the medical notes that he or she has reviewed the AE/SAE and has provided an assessment of causality.

There may be situations when an SAE has occurred, and the Investigator has minimal information to include in the initial report to Indivior or designated representative. However, it is imperative that the Investigator always make an assessment of causality for every event prior to the initial transmission of the SAE data to Indivior or designated representative. The Investigator may change his/her opinion of causality in light of follow-up information and amend the SAE data collection tool accordingly. The causality assessment is one of the criteria used when determining regulatory reporting requirements.

## 11 SERIOUS ADVERSE EVENTS

The Investigator or designee is responsible for identifying, documenting and reporting events that meet the definition of an SAE.

An SAE is any event that meets any of the following criteria:

- death;
- life-threatening;
- inpatient hospitalization or prolongation of existing hospitalization;
- persistent or significant disability/incapacity;
- congenital anomaly/birth defect in the offspring of a subject who underwent study procedures in the current study;
- other: Important medical events that may not result in death, be life-threatening, or require hospitalization, may be considered an SAE when, based upon appropriate medical judgment, they may jeopardize the subject and may require medical or surgical intervention to prevent one of the outcomes listed in this definition. Examples of such events are:
  - intensive treatment in an emergency room or at home for allergic bronchospasm
  - blood dyscrasias or convulsions that do not result in inpatient hospitalization

An AE is considered “life-threatening” if the subject was at immediate risk of death from the event as it occurred; i.e., it does not include a reaction that if it had occurred in a more serious form might have caused death. For example, hepatitis that resolved without evidence of hepatic failure would not be considered life-threatening even though hepatitis can be fatal.

AEs requiring hospitalization should be considered SAEs. Hospitalization for elective surgery or routine clinical procedures that are not the result of AE (e.g., elective surgery for a pre-existing condition that has not worsened) should not be considered AEs or SAEs. If anything untoward is reported during the procedure, that occurrence must be reported as an AE (either “serious” or “non-serious”) according to the usual criteria.

In general, hospitalization signifies that the subject has been detained (usually involving at least an overnight stay) at the hospital or emergency ward for observation and/or treatment that would not have been appropriate in the physician's office or other outpatient setting. Complications that occur during hospitalization are AEs. If a complication prolongs hospitalization or fulfils any other serious criteria, the event is serious. When in doubt as to whether “hospitalization” occurred or was necessary, the AE should be considered serious.

An AE is incapacitating or disabling if the experience results in a substantial and/or permanent disruption of the subject's ability to carry out normal life functions.

